4.2 Inclusion-Exclusion Criteria

4.2.1 Inclusion Criteria

The subjects must meet all of the following criteria to be eligible for the study:

- 1. Subjects willing to comply with the requirements of the study and providing a signed written informed consent.
- 2. Immune-competent adult women 18 years of age and older.
- 3. Body Mass Index (BMI) \geq 18.5 and \leq 25.
- 4. Subjects with intent to undergo treatment to improve appearance of cellulite in the posterior thighs.

- 6. Subject that in the opinion of the PI could benefit from treatment to improve appearance of cellulite.
- 7. Postmenopausal for at least 1 year or (if the subject is of childbearing potential) agrees to use an acceptable form of effective birth control for the duration of the study and is willing to take a urine pregnancy test at the screening visit and prior to all injection visits. Acceptable forms of effective birth control methods include:
 - a. Combined oral contraceptives (estrogens and progesterone) or implanted or injectable contraceptives with a stable dose for at least 28 days prior to the Baseline visit
 - b. Hormonal or copper intrauterine device (IUD) inserted at least 28 days prior to the Baseline visit
 - c. Barrier methods of contraception: condom or occlusive cap (diaphragm or cervical caps) with spermicidal foam/gel/film/cream/suppository
 - d. Bilateral tubal ligation prior to the Baseline visit
 - e. Vasectomized partner (in monogamous relationships) for at least 3 months prior to the Baseline visit
 - f. Strict abstinence (at least one month prior to the baseline visit and agrees to continue for the duration of the study or use acceptable form of birth control).
- 8. Negative urine pregnancy test for females of childbearing potential at screening and all injection visits.

4.2.2 Exclusion Criteria

The presence of any of the following exclusion criteria will exclude a subject from enrollment in the study:

- 1. Known/previous allergy or hypersensitivity to any of the Sculptra constituents.
- 2. Known/previous allergy or hypersensitivity to lidocaine and other local anesthetics, e.g. amide type anesthetics, or topical anesthetics or nerve blocking agents.

- 3. Previous or present multiple allergies or severe allergies, such as manifested by anaphylaxis or angioedema, or family history of these conditions.
- 4. Previous treatment/procedure in or near the treatment area:
 - a. Previous permanent implant, filler, lifting threads, or autologous fat in the treatment area, regardless of time.
 - b. Previous semi-permanent implants exemplified by Calcium Hydroxylapatite (CaHA), poly I-lactic acid (PLLA) in treatment area, regardless of time.
 - c. Previous Hyaluronic acid (HA) filler or collagen filler in the treatment area within 12 months.
 - d. Previous energy based aesthetic procedures (e.g. laser, intense pulsed light, radiofrequency and endermology) in the treatment area within 6 months.
 - e. Previous mechanical (e.g. dermabrasion, needling) or chemical aesthetic procedures (e.g. chemical peel) in the treatment area within 6 months.
 - f. Previous treatment with cryotherapy, lipolytic treatments or liporeduction massage in the treatment area within 6 months.

OR is planning to undergo any of these procedures affecting the treatment area, at any time during the study.

- 5. Previous surgery in or near the treatment area, including but not limited to buttock lift or liposuction.
- 6. Scar or skin coloring/bleaching/tattoo that obscures evaluation of the treatment area.
- 7. Intends to initiate a weight loss program during the study.
- 8. Presence of any disease or lesions near or on the area to be treated, e.g.
 - a. Inflammation, active or chronic infection in or near the treatment area
 - b. Psoriasis, eczema, herpes zoster and acanthosis
 - c. Cancer or precancerous condition (e.g. actinic keratosis)
 - d. Varicose veins, severe stretchmarks or severe cellulitis
 - e. Severe skin laxity, flaccidity, sagging
 - f. Skin condition in the treatment area that in the Investigator's opinion could interfere with the safety or effectiveness of the study product or injection procedure.
- 9. History of bleeding disorders or treatment with anticoagulants or inhibitors of platelet aggregation (e.g. aspirin or other Non-Steroidal Anti-Inflammatory Drugs (NSAIDs)), Omega-3, or Vitamin E within 14 days before treatment. Note: Omega-3 and Vitamin E are acceptable as part of a standard multivitamin formulation.
- Treatment with systemic retinoids within 6 months of the Baseline visit, chemotherapy, immunosuppressive agents, immunomodulatory therapy (e.g. monoclonal antibodies or antiviral treatment for Human Immunodeficiency Virus (HIV) or Hepatitis C). Systemic corticosteroids (inhaled corticosteroids are allowed) within 3 months before treatment.
- 11. Use of topical corticosteroids, topical prescription retinoids or cellulite cream in the treatment area within 1 month of the Baseline visit.
- 12. History of cancer or previous radiation near or on the area to be treated.
- 13. HIV positive or active hepatitis.
- 14. History of or active collagen diseases such as systemic lupus erythematosus, rheumatic arthritis, polymyositis, dermatomyositis, skin or systemic scleroderma.
- 15. Tendency to form keloids, hypertrophic scars, or any other healing disorder.
- 16. Woman who is pregnant (confirmed by positive urine pregnancy test/serum pregnancy test), breast feeding or intend to become pregnant over the duration of the study.
- 17. Any medical condition that, in the opinion of the Treating Investigator, would make the subject unsuitable for inclusion (e.g. a chronic, relapsing or hereditary disease, history of disc hernia or lower back pain that may interfere with the outcome of the study).
- 18. Other condition preventing the subject from entering the study in the Treating Investigator's opinion, e.g. subjects not likely to avoid other cosmetic treatments in

the treatment area, subjects anticipated to be unavailable or incapable of understanding the study assessments or having unrealistic expectations of the treatment result.

- 19. Study center personnel, close relatives of the study center personnel (e.g. parents, children, siblings, or spouse), or employees and close relatives of employees at the Sponsor company.
- 20. Participation in any interventional clinical study within 30 days of screening.

4.3 Subject Randomization

This is a non-randomized, open-label, single-arm study.

4.4 Sample Size

The sample size of approximately 30 subjects is not based on a statistical calculation. The selected number of subjects is regarded as enough for an evaluation of safety and effectiveness in this pilot study.

5 General Considerations

5.1 Presentation

Individual subject data obtained from electronic case report forms (eCRFs), central laboratories, local laboratories, external sources, and derived data will be presented in data listings by subject. All data listings that contain an evaluation date will contain a relative study day.

All outputs will be incorporated into Microsoft Word rich text format (.rtf) files, sorted and labeled according to the International Council for Harmonisation recommendations, and formatted to the appropriate page size(s).

Tabulations will be produced for appropriate demographic, baseline, effectiveness, and safety parameters. Tabulations will be organized by using columns for each visit, and rows for each parameter where appropriate.

For categorical variables, summary tabulations of the number and percentage of subjects within each category (with a category for missing data) of the parameter will be presented. Percentage calculations will be based on non-missing data, unless otherwise specified. Percentages are rounded to 1 decimal place, unless otherwise specified.

For continuous variables, the number of subjects, mean (arithmetic), standard deviation (SD), median, minimum, and maximum values will be presented. The precision of summary statistics, unless otherwise specified, will be as follows: mean and median to 1 more decimal place than the raw data and SD to 2 decimal places more than the raw data. In general, the decimal places should not exceed 3 decimal places unless appropriate. Confidence Intervals (CIs) will be provided and will be rounded to 1 more decimal place than the raw data, unless otherwise specified in the table shell.

For ordinal variables, the summary procedures for both categorical and continuous variables will be followed where appropriate.

5.2 Data Conventions

The precision of original measurements will be maintained in summaries, when possible.

For tables where rounding is required, rounding will be done at the final stage of the calculation to the nearest round-off unit. For example, when rounding to the nearest integer, values \geq XX.5 will be rounded up to XX + 1 (e.g., 97.5 will round up to 98), while values <XX.5 will be rounded down to XX (e.g., 97.4 will round down to 97).

Percentages based on frequency counts will be based on available data, and denominators will generally exclude missing values, unless otherwise stated. For frequency counts of categorical variables, categories whose counts are zero will be displayed for completeness. For example, if none of the subjects discontinue due to "lost to follow-up," this reason will be included in the corresponding table with a count of 0. Percentages based on frequency counts of eCRF collections (e.g., demographic categories) will be presented as a whole number (no decimal places), and nonzero values less than 0.5% will be presented as "<1%." Values less than 100% but that round up from 99.5% to 100% will be presented as ">99%."

5.3 Timing of Analyses

The statistical analyses will be performed at the end of the study, after the database has been cleaned and locked. However, an interim review of selected effectiveness data will be performed after all subjects have done their month 6 visit, see Section 5.10.

5.4 Analysis Populations

Study populations definitions are provided below. The numbers of subjects in each population and reasons for exclusion will be summarized.

5.4.1 Safety Analysis Set

All safety analyses will be carried-out in the Safety Analysis Set (SAF), consisting of all subjects who were injected in at least one thigh.

5.4.2 Full Analysis Set

The primary effectiveness analysis population will be the Full Analysis Set (FAS), defined as all subjects who were injected in both thighs.

5.4.3 Per Protocol Analysis Set

If there are any clinical study protocol (CSP) deviations considered to have substantial impact on the primary effectiveness outcome, a per protocol (PP) analysis set excluding those subjects may be defined.

5.5 Baseline Definition

Baseline is defined as the last non-missing assessment prior to the first injection of the study device (including unscheduled assessments) in the study.

5.6 Derived and Transformed Data

Variables requiring calculation will be derived using the following formulas:

 Responder rate (%) regarding GAIS will be calculated as (number of subjects (or thighs) being at least improved/number of subjects reporting at the specified visit)*100.

CCI

• Time to onset of an AE will be derived as the start date minus the date of most recent treatment. If the start date is missing, it will be assumed that the AE started on the day of most recent treatment.

• Duration of an AE will be derived as the stop date minus the start date + 1. If the start date is missing, it will be assumed that the AE started on the day of most recent treatment. Completely missing stop date will not be imputed and therefore no duration will be calculated in these cases. Instead, the number of AEs that were ongoing at the end of the study will be given.

Time to return to daily activities after treatment will be derived as the subject diary date/time with the first "Yes" for "Did you feel comfortable returning to daily activities today?" minus the date/time of the corresponding treatment session injection start time, and will be represented in days. Time to feeling comfortable returning to daily activities will be calculated for each diary (treatment session) separately.

Subjects who never report feeling comfortable during each session period will have their response date and time censored at the date and time of their last diary entry in each period.

- Time to onset of pre-defined expected post-treatment events collected using subject diaries will be derived as the first recorded event date minus the date of most recent treatment.
- Days A duration expressed in days between 1 date (date1) and another later date (date2) will be calculated using the following formula: duration in days = date2 – date1 + 1
- Months A duration expressed in months is calculated as the number of days divided by 365.25/12 (approximately 30.4)
- Years A duration expressed in years is calculated as the number of days divided by 365.25
- Change from baseline Change from baseline will be calculated as: Change = post baseline value – baseline value

5.7 Subgroups

No subgroups are defined for this study.

5.8 Visit Windows

All endpoints will be summarized and analyzed by nominal visit as recorded on the CRF. Data collected at unscheduled visits will be listed only, with the exception of baseline data (see Section 5.5).

Study dates outside of visit windows as described in the Schedule of Assessments presented in the Study Protocol will be considered protocol deviations. Methodology for summarizing out-of-window visit durations are described in Section 6.3.1 of this SAP.

5.9 Missing Data

As a general principle, no substitutions will be made for missing data. All analyses will be based on available data. Exceptions are the start and stop dates of AEs and therapies (described below). The imputed dates will be used to determine whether an AE is treatmentemergent and whether a therapy is prior or concomitant. Listings of AEs and therapies will present the actual partial dates; imputed dates will not be shown.

5.9.1 Imputation of Adverse Event Start and Stop Dates

Start date:

- If start date is completely missing, start date is set to date of most recent treatment.
- If (1) year is present and month and day are missing or (2) year and day are present and month is missing:
 - If year = year of most recent treatment, then set month and day to month and day of most recent treatment.
 - If year < year of most recent treatment, then set month and day to December 31st.
 - If year > year of most recent treatment, then set month and day to January 1st.
- If month and year are present and day is missing:
 - If year = year of first dose and
 - If month = month of most recent treatment, then set day to day of most recent treatment.
 - If month < month of most recent treatment, then set day to last day of month.
 - If month > month of most recent treatment, then set day to 1st day of month.
 - If year < year of most recent treatment, then set day to last day of month.
 - If year > year of most recent treatment, then set day to 1st day of month.

Stop date:

If the outcome of the AE was ongoing or unknown, then the rules outlined below will not be applied.

- If stop date is completely missing, stop date is set to date of study discontinuation/end of study date.
- If (1) year is present and month and day are missing or (2) year and day are present and month is missing:
 - If year = year of study discontinuation, then set month and day to month and day of study discontinuation.
 - If year < year of study discontinuation, then set month and day to December 31st.
 - If year > year of study discontinuation, then set month and day to December 31st.
- If month and year are present and day is missing:
 - If year = year of study discontinuation/end of study date and

- If month = month of study discontinuation/end of study date, then set day to day of study discontinuation date.
- If month < month of study discontinuation/end of study date, then set day to last day of month.
- If month > month of study discontinuation/end of study date, then set day to 1st day of month.
- If year < year of study discontinuation/end of study date, then set day to last day of month.If year > year of study discontinuation/end of study date, then set day to 1st day of month.

5.9.2 Imputation of Prior and Concomitant Therapies Start and Stop Dates Start date:

- If start date is completely missing, start date will be imputed with the informed consent date.
- If year is present and month and day are missing, set month and day to January 1.
- If year and day are present and month is missing, set month and day to January 1.
- If year and month are present and day is missing, set day to the 1st day of month.

Stop date:

- If end date is completely missing, end date will not be imputed and therapy will be assumed to be ongoing.
- If year is present and month and day are missing, set month and day to December 31st.
- If year and day are present and month is missing, set month and day to December 31st.
- If year and month are present and day is missing, set day to the last day of month.

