# 7.2.5.3 Recording instructions for adverse events

Each subject should be questioned about AEs at each study visit following the screening visit. All AEs, non-serious as well as serious, are to be reported as an AE in the eCRF.

The question asked should be: "Since your last clinical visit; have you had any health problems?". Information on AEs can also be obtained from signs and symptoms detected during each examination or from a laboratory test, observations made by the study center personnel, subject diaries, or spontaneous reports from the subjects or their relatives.

When an AE is related to a device deficiency (refer to Section 7.2.10), including technical device malfunction, the AE shall be recorded on the AE form/module in the eCRF and the technical complaint shall be reported separately on the clinical study complaint form, provided in the investigator file, and in the eCRF.

Investigators, or other study center personnel, shall record all AEs in the eCRF, including:

- a) Event term (recorded in standard medical terminology and avoiding abbreviations)
- b) Affected area
- c) Start date (first day with symptoms)
- d) Stop date (last day with symptoms)
- e) Intensity (mild, moderate, or severe according to definition in Section 7.2.5.4)
- f) Seriousness (serious or not serious, according to definition in Section 7.2.5.2)
- g) Causal relationship to study product or study product injection procedure (yes or no)
- h) Action taken (none, medication treatment, non-pharmacological treatment, or other procedures/tests, subject withdrawn)
- i) Outcome of the AE (ongoing, recovered, recovered with sequelae, death, chronic/ stable, not recovered at the end of the study)

The AE form/module in the eCRF must be signed and dated by the Investigator.

<sup>II The term "life-threatening" in the definition of "serious" refers to an event in which the patient was at risk of death at the time of the event; it does not refer to an event which hypothetically might have caused death if it were more severe. (Source: ICH-E2A clinical safety data management: definitions and standards for expedited reporting).

III Planned hospitalization for a pre-existing condition, or a procedure required by the CSP, without serious deterioration in health, is not considered a SAE. (Source: ISO14155:2011).

2021-08-25 16:18

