#### 8.4 Data Transformations

Responder rate (%) regarding GAIS will be calculated as (number of subjects (or thighs) being at least improved/number of subjects reporting at the specified visit)\*100.

Time to onset of an AE will be derived as the start date minus the date of most recent treatment. If the start date is missing, it will be assumed that the AE started on the day of most recent treatment.

Duration of an AE will be derived as the stop date minus the start date + 1. If the start date is missing, it will be assumed that the AE started on the day of most recent treatment. Missing stop date will not be imputed and therefore no duration will be calculated in these cases. Instead, the number of AEs that were ongoing at the end of the study will be given.

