# 8.7 Handling of missing data

Study data will be presented on observed cases, i.e.no imputation of missing values will be performed. Exception: when calculating duration and time to onset for AEs where start date is missing. If the start date is missing, it will be assumed that the AE started on the day of most recent treatment.

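### SAP 5.9.1 imputes a completely missing AE stop date that SAP 5.6 and protocol 8.4 leave missing, and its month-known start-date rule tests the wrong treatment year, so some AEs meet no rule

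*SAP*

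**What the plan says.** **Stop date.** SAP 5.9.1 gives this rule: "If stop date is completely missing, stop date is set to date of study discontinuation/end of study date". It is preceded by an exemption: "If the outcome of the AE was ongoing or unknown, then the rules outlined below will not be applied". SAP 5.6 says: "Completely missing stop date will not be imputed and therefore no duration will be calculated in these cases", and continues: "Instead, the number of AEs that were ongoing at the end of the study will be given". Protocol 8.4 agrees with SAP 5.6: "Missing stop date will not be imputed and therefore no duration will be calculated in these cases". Protocol 8.7 rules out imputation in general and names one departure: "Exception: when calculating duration and time to onset for AEs where start date is missing". SAP 9 records no changes to the protocol.

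The AE outcomes that protocol 7.2.5.3 asks sites to record are: "Outcome of the AE (ongoing, recovered, recovered with sequelae, death, chronic/ stable, not recovered at the end of the study".

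On the purpose of imputed dates, SAP 5.9 says: "The imputed dates will be used to determine whether an AE is treatmentemergent and whether a therapy is prior or concomitant". SAP 8.1 defines treatment-emergence by when the AE started relative to the first treatment.

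**Start date.** When month and year are known and only the day is missing, SAP 5.9.1 has three branches. The equality branch compares the AE year with the year of the first dose. The earlier-than and later-than branches compare it with the year of the most recent treatment. The parallel rule for a missing month uses the most recent treatment in all three branches.

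**The concern.** Time to onset and duration of AEs are named in the first safety endpoint (protocol 3.1.3, SAP 3.2.1). Protocol 8.6 summarises both for related AEs by mean, SD, median, minimum and maximum, and SAP 8.1 lists related AEs that start more than 21 days after the most recent treatment. With about 30 subjects, a few artificial dates could move a mean or a maximum.

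Two programmers could follow different sections of the same SAP for a completely missing stop date and produce different durations. The exemption also does not line up with the protocol's outcome list. It names an unknown outcome, which that list does not contain, and omits two unresolved outcomes: chronic or stable, and not recovered at study end. AEs with these outcomes can correctly have no stop date, so data queries would not clear them.

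The start-date rule cannot be programmed completely as written. For some AEs no branch applies, and the programmer has to make an unwritten choice.

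**Working it through.** The plan states no figure on this point, so the check sets the rules side by side and then works out what each would do.

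**Stop date**

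| Source | Completely missing AE stop date |
|---|---|
| SAP 5.9.1 | Set to discontinuation or end-of-study date, unless outcome is ongoing or unknown |
| SAP 5.6 | Not imputed, no duration; no exception by outcome |
| Protocol 8.4 | Not imputed, no duration |
| Protocol 8.7 | No imputation; only a missing AE start date is excepted |
| SAP 9 | No protocol change declared |

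1. The exemption in 5.9.1 does not reconcile the texts, because SAP 5.6 and protocol 8.4 make no distinction by outcome. On the protocol's list, only the ongoing outcome is exempt. Chronic or stable AEs and those not recovered at study end would be given an end date.
2. SAP 5.9 ties imputed AE dates to treatment-emergence, which SAP 8.1 decides from the start date. The imputed stop date therefore has no stated use. It is either idle or used for duration against SAP 5.6.
3. Size if used for duration. Duration is stop minus start plus 1 (SAP 5.6). A month is 4 weeks (protocol Figure 2), so Month 12 is 12 × 28 = 336 days after baseline, or Day 337, with a window of ±14 days (Day 323 to 351).
   - Onset Day 1: 337 − 1 + 1 = 337 days (323 to 351).
   - Onset at a third session on Day 57 (28-day spacing): 337 − 57 + 1 = 281 days (267 to 295).
   - Onset at a third session on Day 85 (42-day spacing): 337 − 85 + 1 = 253 days (239 to 267).
   - Under SAP 5.6 each of these has no duration. The figures assume the subject reaches the Month 12 visit; earlier discontinuation gives smaller ones.

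**Start date, month and year known**

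1. Let Y be the AE year, F the year of the first dose and R the year of the most recent treatment, read as the last one before onset. The branches are Y = F, Y < R and Y > R. If F < R and Y = R, none applies.
2. This needs a session in the calendar year after the first dose, and an AE in that later year after that session. Sessions are 28 to 42 days apart, so the third falls 56 to 84 days after the first.
   - 28-day spacing: 6 Nov + 56 days (24 + 31 + 1) = 1 Jan. Exposed first treatments: 6 Nov to 31 Dec.
   - 42-day spacing: 9 Oct + 84 days (22 + 30 + 31 + 1) = 1 Jan. Exposed first treatments: 9 Oct to 31 Dec.
   - Both ranges assume all three sessions are given. Sessions 2 and 3 are optional. The range is narrower after two sessions, and a subject with one session is not exposed.
3. Illustration with assumed dates: treatments 10 Dec 2021, 7 Jan 2022 and 4 Feb 2022; AE dated March 2022, day missing. F = 2021 and Y = R = 2022, so no branch applies. Every possible onset lies 25 days (1 Mar) to 55 days (31 Mar) after the third treatment. With equality tested on R, the rule gives 1 Mar, 25 days. Falling back on SAP 5.6's assumption for a missing start gives 4 Feb, 0 days, which would drop a related AE from the late-onset listing.
4. If all three tests use R, exactly one of =, < and > holds for any year, so the gap closes.
5. The reference treatment itself is undefined. If it meant the last treatment overall, then with a first dose on 20 Nov 2021, a last on 15 Jan 2022 and an AE in December 2021, two branches apply (Y = F and Y < R). They give 1 Dec and 31 Dec.

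**The case against.** The strongest reply is that neither slip need change any output. SAP 5.6 is the specific rule for duration, and SAP 5.9 limits imputed dates to treatment-emergence and therapy status. On that reading the stop-date rule is never used. The same limit covers start dates: nothing in SAP 5.6 or protocol 8.7 says that partial-date values from 5.9.1 feed time to onset. This stands, and it makes both effects conditional. It does not remove the contradiction or supply the missing branch.

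A second reply is that SAP section 2 cites an annotated eCRF, which may code an unknown outcome or map unresolved outcomes to ongoing. That is possible. The eCRF is not among the documents, so the mismatch is shown only against the protocol's list.

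A third concerns frequency. Treatment dates are not given, and the gap needs sessions across a year-end together with a missing day. When the month contains a session, it may also be unknowable which treatment preceded onset, so no meaningful count of affected onset days can be given. This stands too.

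**Conclusion.** Both defects are in the text. SAP 5.9.1 contradicts SAP 5.6 and departs from protocol 8.4 and 8.7 without declaring it in SAP 9. Its month-known start-date rule leaves some new-year AEs without a rule.

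A reader might infer that reported AE durations will be inflated to about a year. The documents do not support that: SAP 5.6 bars a duration in these cases, and the 337-day figure (323 to 351) arises only if 5.9.1 is used in its place. A reader might also infer that AEs will be misclassified as not treatment-emergent, or will drop out of the late-onset listing. The first cannot follow from the gap, because it arises only in a year after the first dose, so the AE is treatment-emergent whatever its day. The second requires partial-date values to feed time to onset, which the SAP leaves unsaid.

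The primary endpoint is unaffected. The number of AEs involved is unknown and probably small. Severity: minor.

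**What to change.** Before database lock:

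- (a) Delete the completely-missing stop-date rule from SAP 5.9.1, so that SAP 5.6 and protocol 8.4 govern. For any partial stop-date rules kept, match the exemption to the unresolved outcomes actually recorded.
- (b) In the month-known start-date branch, test equality against the year of the most recent treatment.
- (c) Define the most recent treatment as the last one on or before the latest possible onset date. That date is the earliest of the end of the known month or year, any known stop date, and the date the AE was first recorded. Do not let an imputed start fall after a known stop date or the first-recorded date. The recording date matters: with treatments on 3 Jan, 31 Jan and 28 Feb, and an AE dated January reported on 6 Jan, the month-end alone would give a start of 31 Jan, 25 days after the report. With the cap, the start is 3 Jan.
- (d) State whether time to onset and duration use imputed partial dates, and list any remaining departure from protocol 8.7 in SAP 9.

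The cost is a few lines of SAP text and small programming changes. No new data are needed.
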